5.5.10. Histology (LN Cohort Only)

For participants in the LN cohort who complete an optional post-treatment biopsy at Week 50, changes in histology will be summarized using the central pathology biopsy results.

Activity index and chronicity index scores will be summarized at baseline and each postbaseline time point by treatment group using descriptive statistics for the observed value as well as the change from baseline.

In addition, shift tables will display the change in LN class, C3 staining, C4d staining, and C1q staining from pretreatment renal biopsy to post-treatment renal biopsy.

5.5.11. Slope of eGFR (IgAN Cohort Only)

For the IgAN cohort, slope of eGFR will be computed using a mixed effect model including data through Week 26 or Week 50, respectively. The model will include eGFR as the response variable, random patient effects for intercepts and slopes, fixed categorical effects of treatment group, randomization stratification factor, and treatment group by visit interaction as well as a fixed, continuous effect of visit (study year).

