	Absolute values and change from baseline in ravulizumab concentrations over time
To characterize the potential for immunogenicity of ravulizumab in adult participants with LN or IgAN	Incidence of antidrug antibodies (ADAs) over time
Safety (both cohorts)	
To characterize the safety and tolerability of ravulizumab in adult participants with LN or IgAN	Incidence of adverse events (AEs) and serious adverse events (SAEs) over time
Exploratory (both cohorts)	
To evaluate the efficacy of ravulizumab compared with placebo on hematuria in adult participants with LN or IgAN	Effect on hematuria as measured by: - Absolute value and change from baseline in red blood cells (RBCs) in urine from baseline to Week 26 and Week 50 - Percentage of participants with $< 10 \text{ RBCs}$
To assess quality of life (QoL) based on participant-reported outcomes in adult participants with LN or IgAN based on treatment with ravulizumab compared with placebo	Change from baseline in the 36-item Short Form Health Survey (SF-36v2) at Week 26 and Week 50
	Change from baseline in the 5-level EuroQol-5 Dimension (EQ-5D-5L) at Week 26 and Week 50
To evaluate complement and autoimmune biomarkers in adult participants with LN or IgAN	Absolute values and change from baseline in levels of biomarkers in blood, urine, and kidney tissue at Week 26 and Week 50

Objectives	Endpoints
Exploratory (LN cohort only)	
To assess the efficacy of ravulizumab in exploratory efficacy endpoints	Time to CRR and PRR (using spot UPCR) Percentage of participants with overall renal response at Week 26 and Week 50 (CRR and PRR)
	Time to UPCR > 50% decrease from baseline (using spot UPCR)
To assess QoL based on participant-reported outcomes	Change from baseline in the Functional Assessment of Chronic Illness Therapy (FACIT)-Fatigue score at Week 26 and Week 50
To assess the efficacy of ravulizumab in other exploratory endpoints	Absolute values and change from baseline in anti-double-stranded DNA (anti-dsDNA) and anti-C1q antibodies at Week 26 and Week 50 Histology changes from baseline to Week 50
Exploratory (IgAN cohort only)	
To assess the efficacy of ravulizumab in exploratory efficacy endpoints	Slope of eGFR computed from baseline to Week 26 and Week 50

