5.1.2. Data Presentation for the Extension Period

Data summaries for the Extension Period will be presented by randomized treatment group and overall, if applicable. For the IgAN cohort, summaries will be presented by treatment sequence (ie, “Ravulizumab to Ravulizumab” and “Placebo to Ravulizumab”). In addition, baseline for the IgAN cohort will be defined as the last value prior to their initial exposure to ravulizumab.

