5.4.1. Proteinuria

The percentage change from baseline in proteinuria at Week 50 will be analyzed using a mixed-effect model for repeated measures (MMRM) using all available longitudinal data (either complete or partial). The model will include change from baseline in log-transformed proteinuria as the response variable and fixed, categorical effects of treatment group, randomization stratification factor, visit, and treatment group by visit interaction as well as a fixed, continuous effect of baseline log proteinuria as a covariate. An unstructured covariance matrix will be used to model the correlations among repeated measurements within each participant. If this analysis fails to converge, a first-order autoregressive covariance matrix will be used. The Kenward-Roger approximation will be used to estimate denominator degrees of freedom.

For the IgAN cohort, participants initially randomized to the placebo treatment group will switch to receive ravulizumab at Week 26. Therefore, percentage change from baseline in proteinuria at Week 50 will be summarized descriptively for each treatment group and for each visit from the MMRM analysis, and no formal treatment comparison will be made.

For the LN cohort, the treatment effect will be evaluated using a contrast for treatment group-by-visit term at Week 50. The point estimate and 2-sided 90% CI for the mean difference of log-transformed proteinuria will be back-transformed (via exponentiation) to obtain the GMR and corresponding 2-sided 90% CI. The values will then be expressed as percentage change in adjusted geometric mean of proteinuria at Week 50 relative to baseline.

This analysis will be performed 2 ways:

- Data collected on or after receipt of additional standard-of-care therapy (for the LN cohort only) will be imputed using the value collected at the time of renal flare, extrarenal SLE flare, suboptimal response, and data collected on or after treatment discontinuation will be assumed missing and handled in the MMRM as MAR.
- Data collected on or after receipt of additional standard-of-care therapy or treatment discontinuation will be assumed missing and handled in the MMRM as MAR.

In addition to the proteinuria analyses based on 24-hour urine collections, the percentage change from baseline in spot UPCR at each scheduled visit will be analyzed using an MMRM in a similar manner as above.

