5.5. Tertiary/Exploratory Endpoint Analysis

The exploratory analyses will be based on the FAS. These analyses will be descriptive in nature, and no adjustment for multiplicity will be performed. In addition, there will be no imputation for missing data or data collected on or after the receipt of additional standard-of-care therapy (for LN cohort) or treatment discontinuation unless otherwise specified below.

Summary statistics will be computed and displayed by treatment group and by visit, where applicable. Descriptive statistics for continuous variables will minimally include the number of participants, mean, SD, minimum, median, and maximum. For categorical variables, frequencies and percentages will be presented.

The analyses for participants in the LN cohort and participants in the IgAN cohort will be conducted and reported separately. Participants in each disease-specific cohort will be analyzed as randomized, regardless of actual treatment received.

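### The exploratory IgAN eGFR slope to Week 50 fits one line per arm across the Week 26 switch, so the placebo-arm slope describes neither treatment; the Week 26 slope is not touched by the switch

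*SAP*

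**What the plan says.** SAP 1.1 lists, as an exploratory IgAN endpoint, "Slope of eGFR computed from baseline to Week 26 and Week 50". SAP 5.5.11 gives the model: "slope of eGFR will be computed using a mixed effect model including data through Week 26 or Week 50, respectively". The response is eGFR, with random intercepts and slopes. The fixed terms are "fixed categorical effects of treatment group, randomization stratification factor, and treatment group by visit interaction", plus a "fixed, continuous effect of visit (study year"). There is no change-point, no time-varying treatment term and no baseline covariate.

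SAP 5.4.1 states that "participants initially randomized to the placebo treatment group will switch to receive ravulizumab at Week 26" and, for that reason, that for Week 50 proteinuria "no formal treatment comparison will be made". Section 5.5.11 has no such sentence.

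Three general rules also bear on the point. SAP 5.1 asks for efficacy summaries by study period. SAP 5.1.2 presents IgAN Extension Period data by treatment sequence and says that "baseline for the IgAN cohort will be defined as the last value prior to their initial exposure to ravulizumab". SAP 5.5 says of the exploratory analyses: "These analyses will be descriptive in nature, and no adjustment for multiplicity will be performed".

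**The concern.** A straight line fitted to a path that may bend at Week 26 returns an average of the two segments. In the placebo arm that average mixes on-placebo and on-ravulizumab change, in proportions set by the visit schedule. The number will be reported beside the slope of an arm that took ravulizumab throughout, and readers will subtract one from the other. If the drug alters the rate of eGFR change, that difference understates it. If the drug instead causes a step when it is started, the difference can point the wrong way. The SAP recognises this problem for Week 50 proteinuria but does not carry the safeguard into the slope section.

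**Working it through.** **Plan's own figure.** The documents give no design figure for eGFR slope. The only one is power for Week 26 proteinuria, stated as about 80%. For IgAN, with 36:18 left after 10% dropout, the standard error is 0.60 × √(1/36 + 1/18) = 0.173 and the effect is ln(0.85/0.55) = 0.435. The ratio is 2.51, and 2.51 − 1.645 = 0.87, so power is 80.7% (79.8% with the t distribution). It reproduces, but says nothing about slope.

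**Inputs.**
- IgAN eGFR days (protocol Tables 2 and 4): 1, 15, 29, 71, 99, 127, 155, 183, then 197, 253, 309, 351. Day 8 applies only to participants enrolled before the dose confirmation analysis is complete.
- Switch: Day 183.
- Slopes and variances: none given, so those below are assumptions.

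**Formula.** Let b_P and b_R be the true slopes on placebo and on ravulizumab, with the change occurring at T = 183. The placebo-arm mean path is b_R·t + (b_P − b_R)·min(t, T). With complete data, random intercepts and slopes, and independent errors, the fixed-effect slope equals the least-squares slope, so

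- fitted placebo slope = b_R + (b_P − b_R)·f
- fitted contrast = (b_R − b_P)·f
- f = least-squares slope of g = min(t, T) on t.

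The share kept, f, does not depend on the sizes of the slopes.

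**Numbers, 12 visits from Day 1.** Σt = 1,790, Σt² = 411,052, Σg = 1,412, Σtg = 292,682.
- S_tt = 411,052 − 1,790²/12 = 144,043.7
- S_tg = 292,682 − 1,790 × 1,412/12 = 82,058.7
- f = 82,058.7 / 144,043.7 = 0.570

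| Visits in the fit | Effect at switch | 28 days later | 84 days later |
|---|---|---|---|
| Day 1 on | 0.570 | 0.665 | 0.836 |
| plus Day 8 | 0.593 | 0.684 | 0.846 |
| plus Screening (assumed Day −21) | 0.608 | 0.696 | 0.852 |
| post-baseline only | 0.526 | 0.629 | 0.817 |

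**Illustration.** Assume −6 per year on placebo and −2 on ravulizumab, a difference of 4.0 mL/min/1.73 m² per year. The fitted placebo slope is −2 − 4 × 0.570 = −4.28 and the contrast is 2.28. With Day 8 these are −4.37 and 2.37.

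**Mixed-model check.** One simulated data set of 3,000 patients (1,000 placebo, 2,000 ravulizumab; slope SD 4, residual SD 5) gave a single-line contrast of 2.21. With a knot at Day 183, the pre-switch contrast was 3.64 against a true 4.0. Scaling the knot-model standard errors of 2.26 to 3.57 at 36:18 (slope SD 3 to 6, residual SD 4 to 6) by √[(1/1,000 + 1/2,000)/(1/18 + 1/36)] = 0.134 gives 0.30 to 0.48. The gap of 0.36 is therefore within simulation noise.

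**Acute step instead of a slope effect.** Suppose eGFR drops by 1 unit at first ravulizumab and nothing else changes. On the Day 1 schedule the Week 50 lines have slopes −0.376 (ravulizumab arm) and −1.302 (placebo arm). The contrast is +0.926 per year in favour of ravulizumab (0.585 to 1.397 across the visit sets). The Week 26 fit is also sensitive to such a step, in the other direction: −0.97 per year on the same schedule, and zero if only post-baseline visits enter. That sensitivity has nothing to do with the switch.

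**Precision.** With slope SD 3 to 9, residual SD 4 to 8, 36:18 and a true difference of 4, one-sided 5% power is 0.16 to 0.49 for the single line to Week 50, 0.18 to 0.48 for Week 26 only, and 0.20 to 0.55 for Week 50 with a knot. Longer follow-up offsets much of the dilution, so power is not uniformly worse.

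**Reading of the model.** SAP 5.5.11 places the group-by-visit term among the categorical effects while visit itself is continuous. Protocol 9.4.5.1 has visit categorical and adds baseline eGFR; SAP Appendix 5 does not list the change. A fully categorical interaction would give no single slope per arm, so study-year time and random slopes point to one line per arm. The text should say so.

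**The case against.** The case against has real weight. The comparison free of the switch is already planned: the Week 26 slope is fully placebo-controlled. No Week 50 slope test, contrast or p-value is named, and exploratory analyses are descriptive. A reader might infer that the SAP deals with the switch only for proteinuria. That is wrong: sequence presentation and the baseline reset are general Extension Period rules, so a Week 50 output should carry a placebo-to-ravulizumab label. A reader might also infer that the plan cannot reveal a change of course after the switch. That is true of this one number but not of the plan. SAP 5.4.2 summarizes eGFR at each visit, plots its mean over time and fits the repeated-measures model of 5.4.1, and a bend would show there.

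All of that stands, and it limits the point. It does not remove it. A label does not change what the line estimates. The slope model has no baseline term for the reset to act on. Summaries by period do not help an endpoint defined from baseline through Week 50. The interaction term yields an arm difference whether or not one is named.

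**Conclusion.** The point holds for the Week 50 IgAN slope only. Followed as written, the plan produces a placebo-arm slope that belongs to neither treatment.

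The size is conditional. If ravulizumab changes the slope from the day of the switch, 53% to 61% of the true difference is kept, depending on which early visits enter. On the Day 1 schedule the share rises to about two thirds or 84% with a 28- or 84-day delay. It is tempting to quote a fixed shortfall of about 41% to 43%, but that varies only the Day 8 visit and assumes immediate onset. Nor can the bias be called simply conservative: with no slope effect there is no dilution, and with an acute step the contrast is distorted.

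A reader might go further and take this as a flaw in a planned between-arm test or in the trial's evidence of efficacy. The documents do not support that: the endpoint is exploratory, and no primary or confirmatory result changes. The harm is to interpretation.

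**What to change.** In SAP 5.5.11:

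1. State that any between-arm slope contrast comes from the Week 0-26 data only.
2. For Week 50, add a linear-spline knot at Week 26 (Day 183) and report pre- and post-switch slopes by treatment sequence. At minimum, report the Week 50 slope by treatment sequence and state that no between-arm comparison is made, as SAP 5.4.1 does for proteinuria.
3. State that the group-by-visit term uses continuous time, and list the departure from the protocol's slope model in Appendix 5.

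The knot costs one extra fixed effect and its interaction, with no new data. Its downside is imprecision: the post-switch slope in the placebo-to-ravulizumab sequence rests on about 20 participants and four scheduled eGFR visits after the switch. The minimum option costs one sentence.

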5.6. Safety Analyses

All safety analyses will be performed on the Safety Set and will be based on the actual treatment received. All safety data will be provided in patient listings by treatment group.

AEs will be coded in MedDRA V 23.0 or higher and presented by MedDRA system organ class (SOC) and preferred term (PT).

No formal hypothesis is planned. Safety data will be presented separately for the Initial Evaluation Period, Extension Period, and Post-treatment Follow-up Period.

5.6.1. Extent of Exposure

Study intervention duration, compliance, and exposure will be summarized overall and by treatment group using the Safety Set.

Treatment duration will be calculated (in weeks) starting from the reference day and summarized using descriptive statistics for continuous variables.

Treatment compliance will be calculated as a percentage based on the number of infusions received out of the number of infusions expected.

Exposure will be calculated as the total number of infusions received and summarized using descriptive statistics for continuous variables as well as using number and percentage of participants in each category.

In addition, the total number of participants with missed infusions and reasons for missed infusions (COVID-19 related and other) will be summarized by treatment group and overall. A by-participant listing of patients with missed infusions due to COVID-19 will also be produced.

5.6.2. Adverse Events

The following definitions will be used for AEs:

- **Pretreatment AE:** Any AE that starts after providing informed consent, but before the first infusion of study intervention (ravulizumab or placebo).
- **Treatment-emergent adverse event (TEAE):** Any AE that starts between the start of the first infusion of study intervention and up to 56 days after the last infusion of study intervention.
- **Treatment-emergent SAE (TESAE):** A TEAE that is serious.
- **Post-treatment AEs:** Any AE that starts 56 days or later after the last infusion of study intervention.

All AEs will be coded using MedDRA V 23 or higher and will be summarized by SOC and PT overall, by severity, and by relationship to treatment. Participants having multiple AEs within a category (eg, overall, SOC, PT) will be counted once in that category. For severity/relationship tables, the participant's highest grade/most related event within a category will be counted.

TEAEs and SAEs will be summarized descriptively by treatment group. Percentages will be based on the number of treated participants in the Safety Set within a treatment group. Tables will be sorted by alphabetic order of SOC and by descending frequency of PT within an SOC.

Pretreatment and post-treatment AEs will be provided in by-participant listings and will not be included in summary tables.

In addition, AEs that occur after the receipt of additional standard-of-care therapy will be provided in a separate listing.

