During the 24-week Extension Period, participants in the LN cohort will continue to receive their randomized allocation of study intervention (ravulizumab or placebo) q8w. For the IgAN cohort, participants in the placebo treatment group will receive a blinded loading dose of ravulizumab at Week 26, and participants in the ravulizumab treatment group will receive a blinded ravulizumab dose of 900 mg at Week 26. Starting at Week 28, all participants in the IgAN cohort will receive open-label weight-based doses of ravulizumab q8w until the end of the Extension Period.

During the 36-week Post-treatment Follow-up Period, all participants will continue to receive standard of care and will be monitored for safety, clinical events of interest, and kidney function. Participants who discontinue study intervention early and agree to remain in the study should continue to attend their scheduled protocol visits until Week 50. During these visits, all assessments except for administration of study intervention should be performed according to the Schedule of Assessments. Participants who withdraw from the study will be followed for safety until 8 weeks after the last dose of study intervention. The end of study is defined as the last participant's last visit in the Post-treatment Follow-up Period.

In the LN cohort, participants will receive additional standard-of-care therapy in the event of a protocol-defined renal flare or severe extrarenal SLE flare. After Week 26, participants may also receive additional standard-of-care therapy for protocol-defined suboptimal response.

The primary objective of the study is to evaluate the efficacy of ravulizumab compared with placebo to reduce proteinuria in adult participants with LN or IgAN.

Figure 1: Study Design Schematic – LN Cohort

[figure not shown]

Note: Randomization will be stratified by whether corticosteroid induction treatment was initiated prior to Screening versus during the Screening Period. Allowed concomitant therapy consists of corticosteroids and mycophenolate mofetil. Weight-based dosing regimen (see [Protocol Section 1.1](#)) will be based on the last recorded study visit body weight.

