	
 – IC #16: Compliance with stable and optimal dose of RAS inhibitor treatment for \geq 3 months prior to Screening – EC #1: eGFR $<$ 30 mL/min/1.73 m² during Screening 
3. For LN cohort, received appropriate additional standard-of-care therapy, if required per protocol, during the 26-week Initial Evaluation Period
 
4. Received appropriate allowed concomitant therapy during the 26-week Initial Evaluation Period
 
5. Received all planned number of doses during the 26-week Initial Evaluation Period
 
6. Received correct treatment per randomization schedule
 
7. Did not receive any disallowed medications or therapies during the 26-week Initial Evaluation Period (see Protocol Section 6.7.2)
 
8. Was not unblinded to treatment allocation during the 26-week Initial Evaluation Period
 
Inclusion in the PPS will be determined for each participant prior to database lock.

Safety Set	All participants who receive at least 1 dose of study intervention. Participants will be analyzed according to the study intervention they actually received for reporting exposure and safety data.
PK Analysis Set	All participants who receive at least 1 dose of study intervention and who have evaluable PK data.
PD Analysis Set	All participants who receive at least 1 dose of study intervention and who have evaluable PD data.

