5.6.2.2. AEs and SAEs by SOC and PT

The number of TEAEs and TESAEs and the number and percentage of participants with events will be presented by SOC and PT. Patients are counted once in each SOC and PT. Percentages will be based on the total number of treated patients in the treatment group. SOCs will be listed in descending order of frequency of occurrence.

Additional summary tables stratifying AEs by age, gender, and race will also be provided.

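### Extension Period adverse event percentages have no denominator of their own; the stated rule would count participants not dosed in that period, a 10% relative understatement if 10% leave before Week 26

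*SAP*

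**What the plan says.** SAP 5.6 sets both the population and the layout: "All safety analyses will be performed on the Safety Set and will be based on the actual treatment received", and "Safety data will be presented separately for the Initial Evaluation Period, Extension Period, and Post-treatment Follow-up Period". SAP 4 defines the Safety Set as "All participants who receive at least 1 dose of study intervention", with no condition on when the dose was given.

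The denominator is stated twice. SAP 5.6.2 has "Percentages will be based on the number of treated participants in the Safety Set within a treatment group", and SAP 5.6.2.2, for the tables by system organ class and preferred term, has "Percentages will be based on the total number of treated patients in the treatment group". Sections 5.6.2.3 and 5.6.2.4 refer back to that layout. Neither SAP 4 nor Protocol 9.3 defines a set for participants who enter the Extension Period.

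Under SAP 5.6.2, a treatment-emergent event (TEAE) must begin no earlier than the first infusion and no later than 56 days after the final one. Events outside that window are handled differently: "Pretreatment and post-treatment AEs will be provided in by-participant listings and will not be included in summary tables".

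Only one group changes drug at Week 26. In the IgAN cohort, "participants in the placebo treatment group will receive a blinded loading dose of ravulizumab at Week 26"; the LN cohort stays on its randomized drug (SAP 1.2).

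**The concern.** A table restricted to one period should divide by the people who could have had an event in that period. The rule as written divides by everyone ever treated in the group. Someone who left during the first 26 weeks, or stopped study drug then, would be counted in the Extension Period denominator but could hardly ever appear in the numerator.

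The IgAN placebo-to-ravulizumab column is where this matters most. Its Extension Period table is the trial's picture of adverse events on first ravulizumab exposure in people who had been on placebo. On the literal rule, its denominator would include people who left on placebo and never received ravulizumab. Their inclusion can only lower the percentages. If the share leaving differed between groups, the columns would also be diluted by different amounts.

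**Working it through.** **The plan's own figure.** The documents state no Extension Period denominator and no adverse event rate, so the only related figure to reproduce is the power statement that carries the 10% dropout (SAP 3). For IgAN, the difference on the log scale is ln(0.85/0.55) = 0.435 and the SD is 0.60. With 10% lost, 20 and 40 become 18 and 36. The standard error is 0.60 × √(1/18 + 1/36) = 0.173, and 0.435/0.173 = 2.51. One-sided power at 0.05 is 80.7% (normal) or 79.8% (t), which matches the stated value of about 80%. For IgAN, therefore, the 10% works as loss from the 26-week analysis. The plan does not say so. The LN power does not reproduce at 18/36 (74.7% by t); that is a separate matter.

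**Who can have an Extension Period TEAE.**
- The last dose before Week 26 is on Day 127 (Protocol Table 9 for IgAN; the 8-weekly schedule from Day 15 gives the same day for LN).
- The TEAE window closes 56 days after the last infusion: 127 + 56 = Day 183.
- Day 183 is the Week 26 dosing day, and that dose starts the Extension Period (SAP 5.1.1).
- So a participant with no dose at or after Week 26 has no TEAE time in the Extension Period, apart from a few days of visit window. Protocol 8.4.1 agrees: after early discontinuation of study drug, adverse events are collected for 8 weeks after the last dose.
- This includes participants who stop drug but keep attending visits. They are not dropouts, so the affected share can exceed the dropout rate.

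**Size.** Reported percentage ÷ at-risk percentage = (number dosed at or after Week 26) ÷ (number ever treated). For the IgAN placebo group of 20:

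| Share not dosed at or after Week 26 | Dosed in the Extension Period | Factor | Relative understatement |
|---|---|---|---|
| 5% (assumed) | 19 | 0.95 | 5% |
| 10% (SAP dropout, all before the Week 26 dose) | 18 | 0.90 | 10% |
| 15% (assumed) | 17 | 0.85 | 15% |
| 20% (assumed) | 16 | 0.80 | 20% |

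At 10%, in percentage points:
- 2 participants with an event: 2/20 = 10.0% against 2/18 = 11.1%, a difference of 1.1 points.
- 9 participants: 9/20 = 45.0% against 9/18 = 50.0%, a difference of 5.0 points.
- All 18: 90% against 100%, the maximum of 10 points.

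The IgAN ravulizumab group (40 to 36) has the same 0.90 factor. As an illustration only, with no source in the documents: if 15% of placebo and 5% of ravulizumab participants left, equal at-risk rates of 50% would show as 0.85 × 50 = 42.5% and 0.95 × 50 = 47.5%.

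**Follow-up Period.** The last LN dose is on Day 295, and 295 + 56 = Day 351 (Week 50). The last IgAN dose is on Day 309, and 309 + 56 = Day 365 (Week 52). Nominally, no LN follow-up event, and only IgAN events in Weeks 50 to 52, can enter a TEAE percentage.

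**The case against.** **The text may not mean this.** The denominator sentences are general and do not mention the Extension Period. SAP 5.6 groups by treatment actually received, and SAP 5.1.2 labels the IgAN Extension Period columns by treatment sequence. Someone who left on placebo never received the placebo-to-ravulizumab sequence, so an analyst could reasonably leave that person out. Table specifications are in a separate Data Presentation Plan (SAP 1), which might set the column totals by period. Part of this stands: a reader might infer that the percentages certainly will be divided by everyone ever treated, and the documents do not go that far. But the sequence label does not settle it. SAP 5.1.1 uses the same label for the Initial Evaluation Period, where the column must hold every treated placebo participant. Nor can actual-treatment grouping help the IgAN ravulizumab group or either LN group, whose early leavers did receive their column's drug. SAP 5.1.2 and 5.4 redefine baseline for the Extension Period but say nothing about the denominator.

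**The effect is small and visible.** About 2 of 20 participants are at issue. For 9 events, the exact 95% intervals are 23.1 to 68.5% (9/20) and 26.0 to 74.0% (9/18), so the shift is well inside sampling error. Counts are printed beside percentages (SAP 5.6.2.1 and 5.6.2.2), disposition is shown by period (SAP 5.2), and no safety hypothesis is tested. All of this stands, and it limits the weight of the point.

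**The alternative has a cost in LN.** LN stays randomized and blinded to Week 50. Requiring a dose at or after Week 26 conditions on a post-randomization event, so the arms are no longer compared as randomized. This stands and shapes the fix.

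**Follow-up.** A reader might infer that Follow-up percentages are diluted too. They are not, because post-treatment events go to listings and stay out of the summary tables.

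**Conclusion.** The point holds for the Extension Period. The only stated denominator is all treated participants, and nothing in the SAP replaces it for a period table. Applied literally, it dilutes Extension Period TEAE percentages in every group, with most consequence in the IgAN placebo-to-ravulizumab group, the only one that switches.

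The 10% is relative, not percentage points. It rests on taking the sample-size dropout as loss before the Week 26 dose and on counting no participant who stops drug but stays on study. A reader might take it as the plan's own Week 26 dropout figure, but the plan attaches no time point to it.

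This is worth correcting before the tables are built. A stated rule would give the wrong denominator for incidence on first ravulizumab exposure, though it would not change any formal conclusion.

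**What to change.** In SAP 4, add an Extension Safety Set: participants who receive at least one dose of study intervention at or after Week 26. In SAP 5.6.2 and 5.6.2.2, name it as the denominator for Extension Period TEAE percentages, at minimum for the IgAN cohort.

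If the set is also used for LN, note that it conditions on a post-randomization event and keep the whole-study Safety Set table alongside. No new Follow-up denominator is needed; it is enough to state that post-treatment events are listed only.

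The cost is one flag and one changed denominator, with no new data. The Extension Period columns will no longer equal the full treated group, so each table should print its own N. The percentages will rise slightly.
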